The study will only be initiated after it has completed review and approval by the Mayo Institutional Review Board (the IRB). Scientific review will initially be conducted by the Endocrine Research Unit and by the Clinical Research Trials Unit, prior to ethical approval by the IRB which will also approve all patient contact material, advertising and consent forms. The latter will be utilized to ensure informed, written consent is obtained at the time of screening where they will meet the principal investigator or a member of the team to ensure that participants meet entry criteria for the study, understand the risks of participation and the goals of the study.

All Mayo IRB approved studies adhere to the Declaration of Helsinki and are conducted in accordance with ICH good clinical practice (GCP) guidelines. [name] in his role as sponsor-investigator will comply with all these guidelines as well as the other applicable regulatory and legal guidelines during study conduct and when obtaining and documenting informed consent.

The nature of the information obtained for the purposes of the study will be explained in detail to each participant at the time of screening. Specifically, none of this information will become part of the medical record and cannot impact the availability and nature of care or access to healthcare. All information will be stored anonymously in the database and only the PI or one of his designates will have access to the data.

Study Hypothesis: Agonism of the GLP-1 receptor by Liraglutide 3mg will increase weight loss and lower blood pressure and LDL-cholesterol compared to placebo after sleeve gastrectomy.

1° Endpoint: Liraglutide administration (3mg daily) to participants after SG produces significantly greater weight loss from baseline compared to that observed in the group after sleeve gastrectomy who receive placebo.

2° Endpoints:

[figure not shown]
- i. Liraglutide administration (3mg daily) to participants after SG produces will achieve weight loss that is inferior to that achieved by RYGB.
- ii. Greater numbers of participants after SG will have an LDL \leq 100mg/dL and a systolic blood pressure \leq 130mmHg results when receiving Liraglutide (3mg daily) compared to placebo.
- iii. Liraglutide administration (3mg daily) to participants after SG produces blood pressure and LDL-cholesterol lowering that is inferior to that achieved by RYGB.

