We propose enrolling 60 non-diabetic adults scheduled for SG and 30 patients undergoing RYGB. Patients scheduled for SG will be randomized to receive Liraglutide (3mg daily) in a double-blind, randomized, placebo-controlled fashion (randomized in a 1:1 ratio). All participants will be followed longitudinally with serial measurement of outcome variables (weight, blood pressure, lipid profile, activity and satiety) over a three year period. Our power calculations suggest that 25 patients per group will be sufficient to accomplish our goals even with a loss of 5 subjects per group to follow up.

Bariatric Sx	2008		2009		2010		2011		2012		2013	
	ND	DM										
RYGB	107	46	166	70	160	63	207	83	184	64	210	59
AGB	9	0	27	0	10	0	34	4	8	2	3	1
SG	0	0	25	0	32	10	62	29	78	25	102	36

Table 1: Total numbers of laparoscopic surgeries performed as 1st procedure at Mayo Clinic. AGB = Adjustable Gastric Banding; ND = Non-diabetic; DM = Diabetic patients.

a) Subjects: A total of 75 patients will be recruited from the Nutrition Clinic at Mayo Clinic Rochester prior to undergoing bariatric surgery. Of these 25 will be scheduled for RYGB while the remainder (50) are scheduled for SG. Healthy status will indicate that the participant has no known active systemic illnesses or active macrovascular disease. To be eligible subjects must be willing to participate in all the studies outlined. **Baseline Visit:** Subjects will provide written informed consent. To ensure they are healthy, subjects will undergo a history and physical examination including supine and standing blood pressure; blood collection for complete blood count, HbA_{1c}, fasting lipid profile, electrolytes, hepatic panel and urine collection to exclude pregnancy in females of child bearing potential. Habitual activity levels⁴¹, and bowel symptoms⁴² will be assessed.

BMI $\geq 35 \text{ kg/M}^2$ in the presence of at least one weight-related comorbid condition including hypertension, obstructive sleep apnea or dyslipidemia. Alternatively, a BMI $\geq 40 \text{ kg/M}^2$ without comorbid conditions is deemed to confer eligibility for bariatric surgery at the Mayo Clinic.

ii. Age will be between 20 and 65 years of age.

- iii. Subjects will have no active physical illness which will interfere with mobility or weight loss after bariatric surgery.

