e) Randomization: Subjects undergoing SG will be randomized (1:1) at the time of the 3 month visit after bariatric surgery. A double-blind design will be utilized. Liraglutide will be started at 0.6 mg SUBQ daily for 1 week. Subsequently, Liraglutide will be increased by 0.6 mg SUBQ daily on a weekly basis till the maintenance dose of 3.0 mg/day is reached. The placebo dose will also be titrated in a similar fashion. The study medication will be dispensed by the research pharmacy which will handle randomization and ensure that blinding is maintained. SG subjects will return to the CRTU for dispensing of study drug at standard follow-up visits (months 6, 12, 24, 36) and also at months 18 and 30. Subjects undergoing RYGB will return to the CRTU at standard follow up visits, months 3, 6, 12, 24, 36. Recruitment will continue till 50 subjects after SG are randomized and 25 subjects after RYGB are enrolled.

f) Study Visits: These will be timed to coincide with the standard follow-up visits at 3, 6, 12, 24 and 36 months after bariatric surgery. In addition to a history and physical examination, blood will be collected for creatinine, fasting glucose, HbA_{1c}, fasting lipid profile and hepatic panel, and urine collection to exclude pregnancy in females of child bearing potential. Supine and standing blood pressure will also be measured as well as body composition using DXA (at months 12, 24 and 36). Habitual activity levels⁴¹, bowel symptoms⁴², Stunkard's Eating Inventory⁴³, The Weight Efficacy Life-Style Questionnaire⁴⁴ & Eating and Weight Patterns-Revised⁴⁵ will be assessed. Collected data will include height, weight, blood pressure, pulse rate, medications used, and adverse events. During clinic visits, as per standard practice, subjects will meet with a dietitian and with a behavioral psychologist. Compliance will be assessed using an electronic record of food intake. The psychologist will use motivational enhancement and behavior change techniques to promote compliance with the dietary guidelines⁴⁷. In addition, to ensure compliance with instructions to increase physical activity, which will be reiterated at each visit, we will gather information about daily step counts from step-counters or smartphones.

g) Telephone follow up: The study coordinator will schedule monthly calls with each subject (or more frequently if necessary) to rapidly identify problems and help ensure compliance.

h) Early Termination

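### The randomised test of BP and LDL lowering is listed as an at-target count but decided by an undefined rule; add ANCOVA on the month-3 value and keep the count

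*Combined protocol and SAP*

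**What the plan says.** - **Study Hypothesis.** Liraglutide 3 mg "will increase weight loss and lower blood pressure and LDL-cholesterol compared to placebo after sleeve gastrectomy". For BP and LDL this is a statement about size of change, against placebo.
- **2° Endpoints, ii.** "Greater numbers of participants after SG will have an LDL" at or below 100 mg/dL and a systolic pressure at or below 130 mmHg on liraglutide than on placebo. The wording does not settle whether a participant must meet both targets or whether each target is counted separately.
- **2° Endpoints, iii.** This one is worded as lowering, but its comparator is the RYGB group, and under d) Surgery the procedure is chosen on clinical grounds, not by randomisation.
- **1) Interpretation.** Hypothesis (ii) is accepted if adding liraglutide betters what sleeve gastrectomy does for cholesterol and blood pressure. No scale, model, visit or BP posture is given.
- **Statistical Considerations.** Every calculation concerns weight. Intention to treat is stated.
- **Research Design and Methods.** Participants have "serial measurement of outcome variables (weight, blood pressure, lipid profile, activity and satiety) over a three year period".
- **e) Randomization.** "Subjects undergoing SG will be randomized (1:1) at the time of the 3 month visit after bariatric surgery".
- **f) Study Visits.** "These will be timed to coincide with the standard follow-up visits at 3, 6, 12, 24 and 36 months after bariatric surgery". Fasting lipids, supine and standing BP, and medications are recorded at these visits.

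**The concern.** The plan gives two different bases for deciding 2°(ii). The endpoint list says a count at target; the Interpretation section says an improvement on no stated measure. A joint count, two separate counts or a continuous comparison would each fit some part of the text, and they need not agree.

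The count also fits the hypothesis imperfectly. It discards how far LDL or BP moved, and a joint count cannot show which of the two moved. Some participants may already be at target when randomised: raised LDL or BP is not an entry requirement, since a BMI of 40 or more "without comorbid conditions is deemed to confer eligibility for bariatric surgery at the Mayo Clinic", and randomisation follows three months of post-surgical weight loss. Such participants cannot newly reach the target.

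At stake is the precision and clarity of the only randomised evidence on BP and LDL, using data the trial already collects.

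**Working it through.** **1. The plan's own figure.** Statistical Considerations: difference 7.0, SD 8.7, 25 per group, two-sided 0.05. Standardised effect 7.0/8.7 = 0.80; noncentrality 0.805 × √(25/2) = 2.84; df 48. Power is 79.6%, so the stated figure of about 80% reproduces. It is for weight; there is no BP or LDL figure to reproduce.

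**2. Assumptions (none from the documents).**
- Normal outcomes, LDL and BP independent.
- Shift d of 0.80 SD (borrowed from the weight calculation), 0.50 or 0.30 SD.
- Correlation r between the month-3 and outcome-visit values of 0.3, 0.5 or 0.7.
- Proportion p0 of placebo participants at each target of 30%, 50% or 70%.
- 25 analysed per arm, two-sided tests.

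**3. Formulas.**
- ANCOVA: noncentral t, effect d/√(1−r²), df 2n−3. Example, d = 0.80, r = 0.5: 0.80/√0.75 = 0.924; noncentrality 0.924 × √12.5 = 3.27; power 89%.
- Single-target count: p1 = Φ(Φ⁻¹(p0) + d); chi-square test, power by enumerating both binomials. At d = 0.80, p0 of 0.30, 0.50 and 0.70 become 0.609, 0.788 and 0.907.
- Joint count: multiply the two proportions. Example, both 50%: 0.25 against 0.788² = 0.621.
- Holm, both declared: P₀.₀₅² − (P₀.₀₅ − P₀.₀₂₅)². Example, d = 0.80, r = 0.3: 0.827² − 0.087² = 0.68.
- Holm, at least one declared: 1 − (1 − P₀.₀₂₅)². Same case: 1 − 0.260² = 0.93.

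**4. Power at 25 per arm** (ANCOVA rows at r = 0.3/0.5/0.7; count rows are ranges over p0, tested at 0.05 unless marked).

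| Test | 0.80 SD | 0.50 SD | 0.30 SD |
|---|---|---|---|
| ANCOVA, one variable, 0.05 | 83/89/97% | 44/52/68% | 19/22/31% |
| ANCOVA, first Holm step, 0.025 | 74/83/95% | 33/40/57% | 12/15/21% |
| Single-target count | 48–65% | 25–31% | 13–16% |
| Single-target count, 0.025 | 36–53% | 17–22% | 8–10% |
| ANCOVA + Holm, at least one declared | 93/97/99.7% | 55/64/81% | 23/27/38% |
| ANCOVA + Holm, both declared | 68/79/95% | 18/25/45% | 3/4/9% |
| Joint count, both variables shift | 70–81% | 31–44% | 14–20% |
| Joint count, one variable shifts | 9–39% | 7–19% | 6–11% |

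**5. Reading the table.**
- At equal alpha, ANCOVA leads the single-target count in every cell.
- With Holm on ANCOVA and none on the count, the lead can go: at 0.30 SD and r = 0.3, 12.4% against 12.6–15.8%.
- Against a joint count with both variables shifting, at least one Holm rejection is ahead throughout, but requiring both is not: 68–95% against 70–81% at 0.80 SD, 18–45% against 31–44% at 0.50 SD.
- If only one variable shifts, the joint count is weak throughout.

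**6. Fewer analysed.** Research Design and Methods says "25 patients per group will be sufficient to accomplish our goals even with a loss of 5 subjects per group to follow up", while e) Randomization says "Recruitment will continue till 50 subjects after SG are randomized and 25 subjects after RYGB are enrolled". Losing 5 from each arm of 25 leaves 20. At 20 per arm and 0.80 SD: single-target count 39–49% at 0.05; first-step ANCOVA 63/72/88%; joint count with both shifting 59–66%; both declared under Holm 53/65/87%.

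**7. What ANCOVA can detect.** At 25 per arm and 0.05, 80% power needs about 0.81 SD unadjusted, so 0.81 × √(1−r²) = 0.77, 0.70 and 0.58 SD for r = 0.3, 0.5 and 0.7.

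**The case against.** The strongest reply is that the plan does not confine itself to the count. BP and lipid profile are listed as serially measured outcomes, and the Interpretation rule would permit a continuous comparison. That stands: a reader might infer that the plan rules one out, and it does not. But permission is not specification. The rule names no measure and does not match the endpoint it is meant to decide.

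Second, the count is a sensible clinical question, and the arms are randomised. That also stands. A reader might infer that the count is biased, or that participants already at target invalidate it. Neither follows: such participants fall to both arms by chance and cost sensitivity, not validity.

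Third, the text joins the two targets with a conjunction and the hypothesis has both variables falling, so the joint, both-shift case may be the intended one. There the power advantage is not assured, as step 5 shows. This limits the claim. A significant joint count, however, does not establish that both variables fell; its nearer counterpart is at least one Holm rejection, which is ahead in every case tried. ANCOVA also gives an estimate for each variable.

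Fourth, every effect, correlation and rate is assumed. That is so, and the figures are illustrations only. Lastly, the primary endpoint also lacks a named model and visit. That is true, but the mismatch over what decides (ii) is specific to this endpoint.

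**Conclusion.** The point holds as a cheap improvement to a secondary endpoint. Two sections differ on what decides 2°(ii), and the hypothesis of lowering has no specified randomised test on its own scale although the data are scheduled. On the assumptions above, at 25 per arm and 0.80 SD, ANCOVA gains roughly 20 to 50 percentage points over a single-target count at 0.05 (83–97% against 48–65%).

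A reader might go on to infer that ANCOVA is always more powerful, or that the gain is certain once the count is per target. The calculations do not support that: it depends on how alpha is shared, on whether the count is joint, and on whether both outcomes must be declared. Nor does the trial become well powered for modest effects. Even ANCOVA needs about 0.58–0.77 SD for 80% power at 0.05, and at 0.30 SD no option exceeds 40%. The result should therefore be read mainly as an estimate with its interval. Independence of LDL and BP is assumed throughout; the true effects are unknown.

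**What to change.** Reconcile 2°(ii) with the Interpretation section as follows.

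- Add LDL and systolic BP as continuous outcomes and name them as the test of lowering. Compare the randomised SG arms, as randomised, by ANCOVA with the month-3 value as covariate. State that this value is taken before the first dose, which the plan does not now say.
- Name one visit (the one named for the primary endpoint or, if none is named, month 36, the last visit) and one BP posture, supine or standing.
- Report adjusted differences with 95% confidence intervals, with Holm across the two outcomes.
- State how values after a change in lipid or BP medication are used; one option is to analyse them as measured and report the changes by arm.
- Keep the 2°(ii) count as a supporting result, and state whether it is joint or per target.
- Rewrite the Interpretation rule for (ii) to refer to these analyses.

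Cost: no new visits or measurements; the endpoint wording changes and a short analysis paragraph is added. The count is no longer the sole named test, and Holm costs some power: at 25 per arm, 0.80 SD and r = 0.3, first-step ANCOVA has 74%, below the 79% of an unadjusted t-test at 0.05. If the sponsor intends a joint target and expects both variables to move, the count alone may do about as well when both ANCOVA results must be declared, unless the month-3 correlation is high.

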compared to the SG + placebo group. Similarly, we will reject our 2° (i) hypothesis if the weight loss observed in participants who undergo SG and receive Liraglutide does not differ from that after RYGB. Such a conclusion would support a role of GLP-1 in the weight loss achieved (and maintained) after RYGB. The questionnaires collected over the duration of the study will be utilized to help generate hypotheses related to food intake as it is affected by liraglutide use after SG compared to placebo. As before, we will determine whether the addition of liraglutide to SG improves effects of SG on cholesterol and blood pressure ¹⁵. If this indeed the case, we will accept our 2° hypothesis (ii). If the high GLP-1 concentrations observed after RYGB modulate appetite and food intake as suggested by our preliminary data (Fig. 1), we would expect weight loss after RYGB to also lower cholesterol and blood pressure. We will reject our 2° (iii) hypothesis if the blood pressure and LDL-cholesterol lowering observed in participants who undergo SG and receive Liraglutide does not differ from that after RYGB.

STATISTICAL CONSIDERATIONS:

Using JMP® Pro 11.2.1 (SAS Institute) for the power calculation we established the following: -

In a prior experiment¹⁵ we observed an overall [mean value \pm (SD)] of % weight change after RYGB = $-26.1 \pm (8.7)$ at 1 year. Assuming similar variation, 25 subjects who complete the study in each group would provide approximately 80% power (at a 2-sided 0.05 α level), to detect a 7.0% difference in weight change between SG + treatment vs. SG + placebo. An intention to treat analysis will be undertaken.

In another, as yet unpublished experiment, 12 subjects studied before and 4 weeks after RYGB lost 11.0 ± 3.4 Kg within 4 weeks. Assuming similar variation, 25 subjects per group would provide approximately 80% power (at a 2-sided 0.05 α level), to detect a difference of a 2.7 Kg in weight between groups.

Schauer et al.¹⁴ observed an overall [mean value \pm (SD)] of weight change after RYGB = $-29.4 \pm (8.9)$ Kg. Assuming similar variation, 25 subjects per group would provide approximately 80% power (at a 2-sided 0.05 α level), to detect a 7.2kg between-group difference.

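### The claim that 25 per group suffices for the study's goals is unsupported for blood pressure and LDL, because every power calculation is for weight

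*Combined protocol and SAP*

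**What the plan says.** All references are to the combined protocol and SAP.

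- **Research Design and Methods, enrolment paragraph:** "Our power calculations suggest that 25 patients per group will be sufficient to accomplish our goals", and this holds "even with a loss of 5 subjects per group to follow up".
- **Specific Objectives:** the single objective covers cardiovascular risk factors as well as weight.
- **Study Hypothesis:** it names weight loss, blood pressure and LDL-cholesterol.
- **2° Endpoints:** (ii) compares at-target counts between liraglutide and placebo: "Greater numbers of participants after SG will have an LDL" at or below 100 mg/dL and a systolic pressure at or below 130 mmHg. (iii) compares the amount of blood-pressure and LDL lowering between sleeve gastrectomy (SG) plus liraglutide and Roux-en-Y gastric bypass (RYGB).
- **Statistical Considerations:** there are five calculations, all for weight. The first says that "25 subjects who complete the study in each group" give about 80% power "to detect a 7.0% difference in weight change between SG + treatment vs. SG + placebo". The other four are also for weight, three in kg and one in per cent.
- **Interpretation:** for (ii) there is an accept rule, "If this indeed the case, we will accept our 2° hypothesis (ii)". For (iii) there is a reject rule, which applies if the lowering is found not to differ from that after RYGB.

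**The concern.** The sentence reports what the power calculations show, and its natural reading covers every stated goal. Nothing in Statistical Considerations addresses an at-target proportion, or a change in blood pressure or LDL. For those endpoints the assurance has no calculation behind it.

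The consequence is most direct for (iii). Its rule turns the absence of a detected difference into a conclusion about SG plus liraglutide against RYGB. Such a rule is informative only if the design could have detected a difference that matters. The only statement that it could is the enrolment sentence.

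**Working it through.** **1. Inputs.** From the document: 25 per group, two-sided alpha 0.05, about 80% power, SG arms "randomized in a 1:1 ratio", and the SDs and differences in the table below. Not in the document: the placebo at-target rate, the SD of blood-pressure or LDL change, any target difference, and the test for (ii) or (iii). These are handled by assumption over a range.

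**2. The plan's own figures.** Two-sample t test with 48 degrees of freedom and noncentrality (difference / SD) × √(n/2). With n = 25, √12.5 = 3.536. For the first calculation, 7.0/8.7 = 0.805, and 0.805 × 3.536 = 2.845, which gives 79.6% power.

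| Weight outcome | Difference | SD | Power |
|---|---|---|---|
| % change | 7.0 | 8.7 | 79.6% |
| kg | 2.7 | 3.4 | 78.6% |
| kg | 7.2 | 8.9 | 80.0% |
| kg | 3.4 | 4.2 | 80.1% |
| % change | 2.5 | 3.0 | 82.3% |

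The weight statements hold.

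**3. Endpoint (ii), a proportion.** For placebo rate p0 and liraglutide rate p1, exact power is the sum over all outcomes (x, y) of b(x; 25, p0) × b(y; 25, p1), counting those outcomes where the test gives p ≤ 0.05. Here b is the binomial probability. Solving for the rise p1 − p0 that gives 80% power, in percentage points:

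| Assumed placebo rate | Uncorrected chi-square | Fisher exact |
|---|---|---|
| 5% | 28.7 | 33.9 |
| 10% | 33.0 | 38.4 |
| 20% | 36.5 | 40.5 |
| 30% | 37.0 | 40.8 |
| 40% | 36.8 | 40.5 |
| 50% | 35.4 | 38.9 |
| 60% | 31.7 | 34.5 |
| 70% | 26.7 | 29.8 |
| 80% | not reachable | not reachable |

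From 80%, even if every liraglutide participant were at target, power would be 76.6% (chi-square) or 38.3% (Fisher).

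**4. Endpoint (iii), a continuous change.** Solving the t-test power equation in step 2 for 80% with 25 per group gives a standardised difference of 0.809, or about 0.81 SD. Without an SD this cannot be turned into mmHg or mg/dL.

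**5. Sensitivity to the number analysed.** These results take 25 observed per group. With 20 per group the standardised difference would be about 0.91 SD; with 30 it would be about 0.74 SD.

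**The case against.** The strongest reply is that blood pressure and LDL are secondary, and that trials are ordinarily powered on the primary endpoint alone. The primary statement in Statistical Considerations is correctly worded and correctly computed, and a reader who turns to it can see that only weight was considered. All of that stands. It is why the remedy is wording rather than more participants. It does not rescue a sentence that attributes to the calculations a sufficiency they do not address.

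Some stronger readings are tempting, and the document does not support them.

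- A reader might infer that 25 per arm has been shown to be too few for (ii). It has not. With no target difference stated, sufficiency is neither shown nor refuted.
- A reader might take 35 to 41 points as a property of the design for all blood-pressure and LDL goals. It depends on an assumed placebo rate of 20% to 50% and on the choice between chi-square and Fisher. It also has no meaning for (iii), which concerns the amount of lowering.
- A reader might infer that a non-significant (ii) would formally be declared a failure. The Interpretation section states only an accept rule for (ii); the no-difference reject rule in this area belongs to (iii).
- A reader might infer that only the primary comparison has support. Several of the weight calculations refer to between-group differences generally, so they also bear on secondary (i).

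**Conclusion.** Wrong as written. The sufficiency claim is supported for the weight comparisons and unsupported for blood pressure and LDL.

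At 25 per group, two-sided 0.05 and 80% power:

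- **Endpoint (ii):** the detectable rise, from chi-square to Fisher, is about 35 to 41 points at assumed placebo rates of 20% to 50%, about 27 to 35 points at 60% to 70%, and about 29 to 38 points at 5% to 10%. It is not reachable at 80%.
- **Endpoint (iii):** the detectable difference is about 0.81 SD.

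The fault is one of scope: no power figure is miscalculated and the primary analysis is not called into question. The point matters because the rule for (iii) would convert a non-significant comparison into a finding.

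**What to change.** **Enrolment paragraph.** Limit the sentence to the weight comparisons. Add that blood-pressure and LDL endpoints (ii) and (iii) are not formally powered, and give the detectable differences above together with the assumed placebo rates, the tests and the SD-unit basis.

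**Interpretation.** Replace the reject rule for (iii) with reporting of the between-group difference and its 95% confidence interval. Report (ii) in the same way. State that a non-significant result on either is not read as absence of a difference. Both sections need to change together: if the reject rule for (iii) stayed, it would contradict the new statement.

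**Cost.** Protocol wording only, with no change in sample size or data collection. The downside is a less favourable claim for the secondary endpoints.

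### Two enrolment targets compete (60 SG + 30 RYGB against 50 + 25), and the plan's stated tolerance of 5 losses per group holds only under the larger one

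*Combined protocol and SAP*

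**What the plan says.** The plan gives its size in three places and its power in a fourth.

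- **Research Design and Methods, enrolment paragraph:** "We propose enrolling 60 non-diabetic adults scheduled for SG and 30 patients undergoing RYGB". The SG patients are allocated 1:1, so this is 30 per group in three groups. The same paragraph adds: "Our power calculations suggest that 25 patients per group will be sufficient to accomplish our goals even with a loss of 5 subjects per group".
- **a) Subjects:** "A total of 75 patients will be recruited from the Nutrition Clinic at Mayo Clinic Rochester prior to undergoing bariatric surgery". The split follows: "Of these 25 will be scheduled for RYGB while the remainder (50) are scheduled for SG".
- **e) Randomization:** "Subjects undergoing SG will be randomized (1:1) at the time of the 3 month visit after bariatric surgery". The stopping rule is: "Recruitment will continue till 50 subjects after SG are randomized and 25 subjects after RYGB are enrolled".
- **Statistical Considerations:** 25 subjects per group who complete the study give about 80% power, two-sided 0.05, for a 7.0-point difference in percentage weight change between SG + liraglutide and SG + placebo. The SD of 8.7 comes from a 1-year result after RYGB. The analysis is to be by intention to treat.

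On outcome collection, f) Study Visits says "Collected data will include height, weight, blood pressure, pulse rate, medications used, and adverse events". For patients who withdraw, h) Early Termination asks for a final set of assessments, including weight, where possible.

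**The concern.** A total of 90 and a total of 75 cannot both be the recruitment target. The difference matters because the enrolment paragraph promises that 25 per group will do even after 5 per group are lost, while Statistical Considerations defines those 25 as completers. A group that starts at 25 cannot lose 5 and still have 25.

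The rule that actually ends recruitment, in e) Randomization, is the version with no margin after randomisation. SG patients who drop out before month 3 are replaced, because recruitment runs until 50 have been randomised. Losses between month 3 and month 36 are not replaced. RYGB patients are counted at enrolment, so that group has no margin at any point.

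At stake are the number randomised for the primary comparison and the plan's assurance about how much attrition the trial can absorb.

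**Working it through.** **Inputs.** Targets of 60/30 (enrolment paragraph) and 50/25 (a) Subjects and e) Randomization); loss of 5 per group (enrolment paragraph); difference 7.0 points, SD 8.7, two-sided alpha 0.05, 25 completers per group (Statistical Considerations).

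**1. Counts.**
- 60 + 30 = 90; 50 + 25 = 75; gap 90 − 75 = 15 (10 SG, 5 RYGB).
- Under 60/30: 60/2 = 30 per SG arm and 30 RYGB; 30 − 5 = 25 per group.
- Under 50/25: 50/2 = 25 per SG arm and 25 RYGB; 25 − 5 = 20 per group.

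**2. The plan's own power figure.** By the normal approximation, n per arm = 2(1.960 + 0.842)² × 8.7² / 7.0² = 24.2, rounded up to 25, with power 81.2% at 25. With the two-sample t-test, the noncentrality is 7.0 / (8.7 × √(2/25)) = 2.845 on 48 degrees of freedom (critical value 2.011), giving 79.6%. The stated figure of about 80% reproduces.

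**3. Power as the number with a usable weight falls.** Same t-test, noncentrality 7.0 / (8.7 × √(2/n)):

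| Per arm with outcome | Power for 7.0 points | Difference detectable with 80% power |
|---|---|---|
| 30 | 86.5% | 6.40 |
| 25 | 79.6% | 7.04 |
| 24 | 77.9% | 7.19 |
| 23 | 76.1% | 7.35 |
| 22 | 74.1% | 7.52 |
| 21 | 72.0% | 7.71 |
| 20 | 69.8% | 7.91 |
| 18 | 65.0% | 8.36 |

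The row for 20 is the stated loss of 5 from 25 with no weight recovered. The row for 18 is 7 lost per arm; that number is an assumption, used only to show that 20 is not a floor.

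**4. A second scenario from the plan.** For SD 8.9 kg and a difference of 7.2 kg, 25 per group gives 80.0% and 20 gives 70.3%. The detectable difference rises from 7.2 to 8.1 kg.

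**5. Can the two targets be read as stages?** Suppose 60 SG patients are enrolled before surgery and 50 reach randomisation at month 3.
- Item a) Subjects recruits only 50 SG patients before surgery, which contradicts this.
- It cannot explain RYGB. That group is not randomised and is counted at enrolment both times, yet the figure is 30 in one place and 25 in the other.
- It would also use the whole SG allowance (60 − 50 = 10, or 5 per arm) before follow-up on study drug begins.

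**The case against.** The strongest reply is that the plan is clearer than the mismatch suggests. Items a) and e) give the same numbers, e) is an explicit stopping rule, and one sentence with its loss clause is out of line. This stands in part: there are two competing targets, not three, and a) and e) part only if SG patients are lost before month 3. It does not remove the problem, because the sentence out of line is the one that carries the attrition assurance.

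A second reply is that losing a patient need not mean losing the outcome. "All participants will be followed longitudinally with serial measurement of outcome variables", the analysis is by intention to treat, and early-termination assessments are sought. This also stands: each weight recovered moves power back up the table. But those assessments are only where possible, no method for missing outcomes is given, and intention to treat restores power only where a weight exists. The power paragraph does not name the analysis visit, and the loss by a given visit is not stated.

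Third, 5 lost from 30 is 16.7%, and 5 from 25 is 20%. At the same rate, about 4 of 25 would be lost (25 × 0.167 = 4.2), leaving 21 and 72.0% power. That is a fair qualification, although the plan states its loss as a count.

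Some stronger readings are tempting but unsupported. A reader might infer that the power calculation is wrong; it reproduces. A reader might infer that the trial has 70% power, or that the shortfall cannot exceed about 10 points (79.6 − 69.8 = 9.8). The first needs all 5 losses per arm to leave no weight, and the second needs losses not to exceed 5; the documents establish neither. A reader might also conclude that 60/30 was intended because it fits the allowance; the documents do not show which target was meant.

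**Conclusion.** The inconsistency is firm and must be resolved whatever its effect on power. The plan has two targets, 15 patients apart, and its tolerance of 5 losses per group is not delivered by its own stopping rule.

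The effect on power is conditional. With 25 randomised per SG arm, power for 7.0 points is about 80% if all 25 provide the outcome. It is about 70% (80% power for about 7.9 points) if the stated 5 per arm are lost after randomisation without a usable weight. Recovered weights put it between those values, and more than 5 lost per arm would put it below 70%. These figures assume a two-sample t-test, equal losses in the two arms and the plan's SD of 8.7, a 1-year value applied to a three-year study.

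RYGB should not be set aside. The sufficiency claim in the enrolment paragraph covers all three groups, so RYGB at 25 has no loss allowance either. Only the 7.0-point statement names the SG + liraglutide against SG + placebo contrast, so the conditional figures above are for that comparison.

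**What to change.** Bring the enrolment paragraph, a) Subjects and e) Randomization to one target. State separately the numbers to be randomised (SG) or enrolled (RYGB) and the numbers expected to complete.

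**Low-cost option: keep the stopping rule in e).**
- In the enrolment paragraph and in a), replace the current figures with: *as many adults scheduled for SG as needed to randomise 50 (25 per arm), and 25 undergoing RYGB*.
- State that 20 per group are expected to complete if 5 per group are lost.
- Replace the loss clause with: *about 80% power for 7.0 points if all 25 per SG arm provide the outcome; about 70% (80% power for about 7.9 points) if 5 per arm are lost without a usable weight*.

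This needs text edits only. It adds no patients to the stopping rule, and the power statement in Statistical Considerations can stand. The drawback is a less favourable stated power, which is already the position under the current rule.

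**If 60/30 was intended.** Change e) to 60 SG randomised (30 per arm) and 30 RYGB enrolled, change a) to match, describe the 60 in the enrolment paragraph as the number randomised, and state 25 per group expected to complete. This adds at least 15 patients (10 SG, 5 RYGB) followed to month 36, plus extra SG enrolment to replace losses before month 3, so it is not the cheap option.
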